5.10. Data Quality Assurance

Completed eCRFs are required for each subject randomly assigned to study drug. Electronic data entry will be accomplished through the ClinSpark® remote electronic data capture system, which allows for on-site data entry and data management. This system provides immediate, direct data transfer to the database, as well as immediate detection of discrepancies, enabling site coordinators to resolve and manage discrepancies in a timely

manner. Each person involved with the study will have an individual identification code and password that allows for record traceability. Thus, the system, and subsequently any investigative reviews, can identify coordinators, investigators, and individuals who have entered or modified records.

Furthermore, the investigator retains full responsibility for the accuracy and authenticity of all data entered into the electronic data capture system. The completed dataset and their associated files are the sole property of the sponsor and should not be made available in any form to third parties, except for appropriate governmental health or regulatory authorities, without written permission of the sponsor.

6. Ethical Considerations

6.1. Ethical Conduct of the Study

This study will be performed in accordance with the recommendations guiding physicians in biomedical research involving human subjects adopted by the 18th World Medical Association General Assembly, Helsinki, Finland, 1964 and later revisions, as well as, United States Title 45 Code of Federal Regulations (CFR) Part 46 GCP, and International Council for Harmonisation (ICH) guidelines describing technical requirements for registration of pharmaceuticals for human use.

6.2. Institutional Review Board (IRB)

After the protocol is finalized and approved by FDA, FDA staff with primary responsibility for the FDA's involvement with the project (i.e., the FDA Project Lead) will submit the protocol and associated documentation to FDA's Office of the Chief Scientist to facilitate an Institutional Review Board Authorization Agreement (IAA) with FDA as the relying institution. The FDA Project Lead or investigator will provide the local IRB (i.e., Advarra) with all required documents, including the study protocol and informed consent form. The study will not be initiated until appropriate IRB approval is obtained from the local IRB. The investigator will provide the FDA Project Lead with copies of the approval documents for the protocol, informed consent form, and all recruiting materials. The sponsor will provide a copy of the local IRB approval letter to the investigator or designee before the study is initiated. The local IRB will also receive copies of any original or amended information sheets or pamphlets given to the study subject in support of the informed consent process and any advertisements or other recruitment material. Such materials will not be employed in the study before approval by the local IRB.

Subjects will be informed that they have the right to contact the local IRB or Office for Human Research Protections if they have any questions, concerns, complaints, or believe they have been harmed by the participation in this research study as a result of

investigator negligence. Subjects will be given the address and phone number of the local IRB.

7. Administrative Procedures

7.1. Responsibilities of the Investigator

The following administrative items are meant to guide the investigator in the conduct of the study but may be subject to change based on industry and government standard operating procedures, working practice documents, or guidelines. Changes may be reported to the IRB but will not result in protocol amendments.

7.1.1 Form FDA 1572

The investigator will complete and sign the Form FDA 1572.

7.1.2 Adherence to Protocol

The investigator agrees to conduct the study as outlined in this protocol in accordance with the ICH E6(R2) and all applicable guidelines and regulations.

7.1.3 Reporting Requirements

By participating in this study, the investigator agrees to submit reports of SAEs according to the time line and method outlined in the protocol (Section 5.7.4.1.2). In addition, the investigator agrees to submit reports to the IRB as appropriate. The investigator also agrees to provide the sponsor with an adequate report shortly after completion of the investigator's participation in the study.

7.1.4 Source Documentation

By participating in this study, the investigator agrees to maintain adequate case histories for the subjects treated as part of the research under this protocol. The investigator agrees to maintain accurate eCRFs and source documentation as part of the case histories.

7.1.5 Retention of Records

The investigator agrees to keep the records stipulated in this protocol and those documents that include (but are not limited to) the study-specific documents, identification log of all participating subjects, medical records, source worksheets, all original signed and dated informed consent forms, subject authorization forms regarding the use of personal health information (if separate from the informed consent form), copies of all eCRFs, query responses, and detailed records of drug disposition, to enable evaluations or audits from regulatory authorities, the sponsor, or its designees.

Furthermore, ICH 4.9.5 requires the investigator to retain essential documents specified in ICH E6(R2) (Section 8) until at least 2 years after the last approval of a marketing application for a specified drug indication being investigated or, if an application is not approved, until at least 2 years after the investigation is discontinued and regulatory authorities are notified. In addition, ICH 4.9.5 states that the study records should be retained until an amount of time specified by applicable regulatory requirements or for a time specified in the clinical study site agreement between the investigator and sponsor.

Refer to the clinical study site agreement for the sponsor's requirements on record retention. The investigator should contact and receive written approval from the sponsor before disposing of any such documents.

7.1.6 Financial Disclosure and Obligations

The investigator is required to provide financial disclosure information to allow the sponsor to submit the complete and accurate certification or disclosure statements required under 45 CFR 46. In addition, the investigator must provide to the sponsor a commitment to update this information promptly if any relevant changes occur during the course of the investigation and for 1 year after the completion of the study.

Neither the FDA nor the study clinic is financially responsible for further testing or treatment of any medical condition that may be detected during the screening process.

7.2. Confidentiality and Disclosure of Data

All subjects will sign a HIPAA-compliant authorization form containing the mandated core elements and requirements before participation in this clinical study. The sponsor and designees affirm and uphold the principle of the subject's right to protection against invasion of privacy. Throughout this study, a subject's source data will only be linked to the sponsor's electronic data capture system database or documentation via a unique identification number. As permitted by all applicable laws and regulations, limited subject attributes such as gender, age or date of birth, and subject initials may be used to verify the subject and accuracy of the subject's unique identification number.

To comply with ICH Guidelines for GCP and to verify compliance with this protocol, the sponsor requires that the investigator allow review of the subject's original medical records (source data or documents) by the study monitor, representatives from any regulatory authority (e.g., FDA), the sponsor's designated auditors, and the appropriate IRB. These medical records will include, but will not be limited to, clinical laboratory test result reports, ECG reports, admission and discharge summaries for hospital admissions occurring during a subject's study participation, and autopsy reports. Access to a subject's original medical records requires the specific authorization of the subject as part of the informed consent process.

Copies of any subject source documents that are provided to the sponsor must have certain personally identifiable information removed (i.e., subject name, address, and other identifier fields not collected in the subject's eCRF).

Data will be maintained and backed up in the electronic data capture system. All access to the data is protected by username and password, and each staff member and all sponsor staff will have separate access that requires a separate username and password. Access is only given to site staff and requested sponsor staff who have completed the appropriate training.

7.3. Subject Consent

Written informed consent in compliance with 45 CFR 46 will be obtained from each subject before entering the study or performing any unusual or nonroutine procedure that involves risk to the subject. An informed consent template may be provided by the sponsor to the study clinic. If any institution-specific modifications to study-related procedures are proposed or made by the study clinic, the consent should be reviewed by the sponsor or its designee or both before IRB submission. Once reviewed, the consent will be submitted by the investigator to the IRB for review and approval before the start of the study. If the informed consent form is revised during the course of the study, all active participating subjects must sign the revised form.

Before enrollment, each prospective subject will be given a full explanation of the study and be allowed to read the approved informed consent form. The informed consent process will be performed by a clinical research nurse in a private room. The subject will be given unlimited time to ask questions regarding study participation, and each subject will be questioned to ensure their understanding. Once the investigator is assured that the subject understands the implications of participating in the study, the subject will be asked to give consent to participate in the study by signing the informed consent form.

The investigator will provide a copy of the signed informed consent form to the subject. The original form will be maintained in the subject's medical records at the site.

7.4. Data Collection

Full details of procedures for data collection and handling will be documented in the data management plan, which is initiated with the final protocol receipt. The data management plan is a changing document that evolves over the course of the study and is finalized by database lock.

7.5. Publications

No information related to or generated by this study will be released to the public until it has been reviewed by the sponsor. The sponsor shall own intellectual rights for the data. Authorship on publications will be determined by standard journal requirements.

8. Study Management

8.1. Release of Study Drug to the Study Clinic

Before the study drug can be released to the study clinic, the following documents will be collected from the study clinic by the clinical research organization, retained in the trial master file, and a study drug shipment approval form will be completed by the clinical research organization:

- Protocol signature page signed by the investigator
- IRB approval of the protocol and informed consent form and IRB membership list
- Completed Form FDA 1572, curriculum vitae, and medical licenses from each investigator
- Financial disclosure and debarment certification from each investigator
- Executed contract with investigator and study clinic

8.2. Monitoring

The sponsor or its designee will monitor the study to ensure that it is being conducted according to the protocol, GCP standards, and applicable region-specific requirements, and to ensure that study initiation, conduct, and closure are adequate. The investigators and the study clinic staff will be expected to cooperate fully with the study monitors and personnel or agents of the sponsor and be available during monitoring visits to answer questions sufficiently and to provide any missing information. The investigators and their institutions will permit direct access to source data/documents for study-related monitoring activities, audits, IRB reviews, and regulatory inspections.

During any on-site visits, the study monitor will:

- Check and assess the progress of the study
- Review all informed consent forms
- Review study data collected
- Conduct source document verification
- Identify any issues and address their resolution
- Verify that the facility remains acceptable
- Conduct study drug accountability

These monitoring activities will be done in order to verify that the:

- Data are authentic, accurate, and complete.
- The safety and rights of the subjects are being protected.

- The study is being conducted in accordance with the currently approved protocol (including any amendments), GCP, and all applicable regulatory requirements.

In addition, the sponsor, designated auditors, and government inspectors must be allowed access to eCRFs, source documents, and other study files that may be required to evaluate the conduct of the study.

8.3. Management of Protocol Amendments and Deviations

8.3.1 Modification of the Protocol

Any changes in this research activity, except those necessary to remove an apparent immediate hazard to the subject, must be submitted to the sponsor or designee and reviewed and approved by the local IRB before implementation. Amendments to the protocol must be submitted in writing to the investigator's IRB for approval before subjects are enrolled into an amended protocol.

8.3.2 Protocol Violations and Deviations

Any significant protocol deviations that the investigator or study clinic staff believes are of major importance (e.g., incorrect randomizations, subject enrolled but not eligible) should be reported to the sponsor and the investigator's IRB as soon as possible.

Significant protocol deviations may include the following:

- Deviations from the inclusion/exclusion criteria that may affect subject safety
- Deviations (omission or delay) of safety monitoring procedures
- Deviations in the administration of the study drug
- Deviations in obtaining informed consent

All subjects who are enrolled and receive the study drug, regardless of whether they have a major protocol violation, must continue to be followed for safety for all follow-up study visits.

9. Appendices

Table 9-1: Schedule of Events by Time Point

	Screening	Check-in / Baseline	Treatment Period																				Enrolment Study	
			1	2	3	4	5	6	7	8	9	10	11	12	13	14	21	28	35	42	49	56	63	
Study Week																								
Study Day	-21 to -2	-1	Pre	1	1	1	1	1	1	1	1	1	1	1	1	1	2	3	4	5	6	7	8	9
Hour				0	0.5	1	2	3	4	6	9	12	16	24										
Visit		1		2		3																		
Outpatient visit																								
In House Residency		X																						
Informed Consent		X																						
Medical History		X																						
Targeted Physical Examination			X	X	X	X	X	X	X	X	X	X	X	X	X	X	X	X	X	X	X	X	X	
Comprehensive Physical Exam		X		X																				
Vital Signs		X		X		X	X																	
Telemetry				X	X	X	X	X																
12-Lead ECG		X		X																				
Clinical Chemistry and Hematology ¹		X		X																				
Urinalysis		X		X																				
HIV Ab, HbsAg, HepC Ab		X																						
SARS-CoV-2 Molecular Test																								
Urine Drug and Alcohol Screen		X		X																				
Pregnancy Test (females only) ²		X		X																				
FSH (females only)		X																						
Drug Administration																								
PK Sample (serum)					X		X	X	X	X	X	X	X	X	X	X	X	X	X	X	X	X	X	
Urine Sample Collection (PD)		X		X																				
Flow Cytometry Sample & Analysis		X		X																				
Genomics (puffy cell)				X																				
Proteomics & Small RNA					X		X	X	X	X	X	X	X	X	X	X	X	X	X	X	X	X	X	
Transcriptomics (plasma)						X	X	X	X	X	X	X	X	X	X	X	X	X	X	X	X	X	X	
Concomitant Medications						X	X	X	X	X	X	X	X	X	X	X	X	X	X	X	X	X	X	
Adverse Events						X	X	X	X	X	X	X	X	X	X	X	X	X	X	X	X	X	X	

	2.3.	Exploratory Objective	7
3.	Stuc	ly Overview	8
	3.1.	Study design	8
	3.2.	Sample size	9
4.	Stuc	ly Endpoints	9
	4.1.	Primary Endpoints	9
	4.2.	Secondary Endpoints	10
	4.3.	Exploratory Endpoints	10
5.	Ana	lysis Populations	10
6.	Data	Screening and Acceptance	11
	6.1.	Handling of Missing and Incomplete Data	11
7.	Gen	eral Statistical Considerations	11
	7.1.	Subject Disposition	12
	7.2.	Demographics and Baseline Characteristics	12
	7.3.	Pharmacodynamic Analyses	12
	7.3.	Peripheral Blood Eosinophils	12
	7.4.	Pharmacokinetic Analyses	13
	7.5.	PK/PD Analyses	13
	7.6.	Exploratory Omics Analysis.	14
	7.7.	Safety Analyses	14
	7.7.	Adverse Events	14
	7.7.2	2 Clinical Laboratory Tests	15
	7.7.3	Wital Sign Measurements	15
	7.7.4	Safety 12-lead Electrocardiograms	15
	7.7.	5 Physical Examinations	15

	7.7.6	Other Safety Data	15
8.	Data Qua	ality Assurance	15
Atta	chment A	. Pharmacokinetic, Pharmacodynamic, and Biomarker Sample Collection Sch	edule
			17
Atta	chment B	Randomization Schedule	18

Table of Abbreviation

Abbreviation	Definition
$\mathrm{AUC}_{0 ext{-}\mathrm{inf}}$	area under the concentration-time curve from time zero to infinity
$\mathrm{AUC}_{0\text{-t}}$	area under the concentration-time curve from time zero to last on-study sample
$\mathrm{AUEC}_{0 ext{-t}}$	area under the effect curve from time zero to last on-study sample
AUEC	area under the effect curve
$pAUEC_{0-t}$	percentage area under the effect curve from time zero to last on-study sample
CL/F	apparent clearance
C_{max}	maximum observed concentration
EC ₅₀	the exposure that gives-half maximal response, model parameter
ED_{50}	the dose that gives-half maximal response, model parameter
E _{max,exp}	maximum PD response, model parameter – concentration analysis
$E_{\text{max,dose}}$	maximum PD response, model parameter - dose analysis
$\Delta Eosinophil_{dec, max}$	maximum decrease from baseline in eosinophils
FDA	Food and Drug Administration
K_{el}	elimination rate
mg	milligram
PD	pharmacodynamic
PK	pharmacokinetic
RNA	ribonucleic acid
SC	subcutaneously
SD	standard deviation
T_{max}	time of maximum concentration (C_{max})
$t_{1/2}$	terminal half-life
V/F	apparent volume of distribution

Change Log

Version	Section	Changes
2	5	Added that 'Subjects who did not complete their treatment (referred to as early termination subjects) will not be included in PK and PD parameter summary calculations.'
2	7.3.1	The descriptive summary for PD parameters is changed from geometric mean to mean. Changes in PD parameter from baseline for placebo and low doses may have negative values and would not allow for calculation of geometric mean. Text describing the primary, secondary, and exploratory PD parameter was updated for clarity.
2	General	Typographical changes included throughout

U.S. Food and Drug Administration Statistical Analysis Plan: SCR-006

1. Introduction

This document outlines the proposed statistical methods for data analysis on data collected from Protocol 'SCR-006: Pharmacodynamic Biomarkers to Support Biosimilar Development: Clinical Study 1 (IL-5 Antagonists – Mepolizumab and Reslizumab)'.

2. Study Objectives

2.1. Primary Objective

The primary objective of this study is to report clinical trial operating characteristics for future clinical pharmacology pharmacokinetic (PK) and pharmacodynamic (PD) similarity studies using different biomarker-based approaches.

2.2. Secondary Objectives

The secondary objectives of this study are:

- To determine the values and variability of PK and PD characteristics at four dose levels (i.e., low, intermediate low, intermediate high, and high doses) for mepolizumab and reslizumab.
- 2. Explore PK and PD relationships using appropriate models for mepolizumab and reslizumab.

2.3. Exploratory Objective

The exploratory objectives of this study are:

- 1. To evaluate the utility of circulating proteins and small RNAs as potential PD biomarkers.
- 2. To inform on the analytical approach and experimental design needed for identifying exploratory proteomic- and small RNA-based PD biomarkers in plasma

3. Study Overview

3.1. Study design

This is a randomized, double-blind, placebo-controlled, single-dose, parallel arm, pilot study. Healthy subjects will be randomized to one of four dose groups (low, intermediate low, intermediate high, and high) of each drug (mepolizumab and reslizumab) or placebo (Table 1). The study will be conducted at one center in the United States (Spaulding Clinical Research unit in West Bend, Wisconsin).

Subjects will report to the study site for screening assessments from days -21 to -2 and then will return to the site on day -1 for baseline assessments. Prior to and following study drug or placebo administration on day 0, they will undergo assessments as described in the Schedule of Events. Subjects will stay in house for the first two weeks and will return to the clinic for study procedures as identified in the Schedule of Events Depending on the treatment arm, subjects will return to the clinic up to 9 times for PK and PD blood draws and additional study procedures as outlined in the Schedule of Events.

All subjects will be sampled daily for the first two weeks and then weekly out to Day 63. Subjects in Groups C, D, G, H, and I will be sampled monthly until Study Day 123. Subjects in Groups A, B, E, and F will follow the Schedule of Events until Day 63 and all other subjects will follow the Schedule of Events until Day 123. Each treatment group should include equal representation of male and female subjects.

Table 1: Study Treatment Groups

Statistical Analysis Plan: SCR-006

Subjects (n)	Treatment Group	Drug
8	A	Mepolizumab low (3 mg)
8	В	Mepolizumab low intermediate (6 mg)
8	С	Mepolizumab high intermediate (12 mg)
8	D	Mepolizumab high (24 mg)
8	Е	Reslizumab low (0.1 mg/kg)
8	F	Reslizumab low intermediate (0.2 mg/kg)
8	G	Reslizumab high intermediate (0.4 mg/kg)
8	Н	Reslizumab high (0.8 mg/kg)
8	I	Placebo

3.2. Sample size

Approximately 86 healthy subjects will be enrolled (72 subjects for treatment and up to 14 potential replacement subjects). Subjects will be randomized to one of 8 different active treatment arms (i.e. 8 per treatment arm) or placebo. This study did not have any formal sample size or power calculations. Doses expected to characterize the dynamic range of the primary PD parameter (eosinophils) were selected. A total of 8 subjects are planned per dose as a typical sample size for estimating values and variability of PK and PD measures in single ascending dose trials.

4. Study Endpoints

4.1. **Primary Endpoints**

- Peripheral blood eosinophil area under the effect curve from time zero to last onstudy timepoint (AUEC_{0-t}, referred to as AUEC for brevity).
- Maximum decrease from baseline in eosinophils (ΔEosinophil_{dec. max})

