6.1. Handling of Missing and Incomplete Data

The following imputation of missing values will be done:

- Pharmacokinetic measurements below the quantification limits will be considered equal to zero for all analyses.
- Non-pharmacokinetic measurements (e.g., eosinophils) below the quantification limits will be considered equal to the lower limit of quantification for all analyses unless explicitly noted otherwise.
- Missing pharmacokinetic or pharmacodynamic data (e.g., skipped outpatient visit) will not be imputed.
- For baseline adjusted measures, samples from Day 1, time 0 will be used for calculating this derived metric. In cases where the Day 1, time 0 sample is missing or invalid, the sample collected at check-in (Day -1) will be used, followed by the screening sample. If none of these samples are available or valid, then no baseline value will be calculated for the subject.

7. General Statistical Considerations

All data will be presented in data listings. Data from subjects excluded from an analysis population will be presented in the data listings, but not included in the calculation of summary statistics. In addition, the reason for exclusion from an analysis population will be noted for individual subjects.

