7.3. Pharmacodynamic Analyses

7.3.1 Peripheral Blood Eosinophils

Individual eosinophil versus time plots will be presented for each participant. For eosinophils, AUEC and maximum decrease from baseline will be calculated for each participant using all on treatment timepoints. Calculations will be performed using non-compartmental analysis packages available in a statistical software. The primary analysis with eosinophils will use pAUEC and maximum decrease from baseline; other derived AUEC measures may be calculated (AUEC calculation without baseline adjustment and with normalization to baseline [pAUEC]) to evaluate how derived PD metrics impact trial design. Baseline adjustments will be based on the average of multiple measurements (i.e., day -1 and day 0, time 0), when available. If only a one of these measures is available, it will be used without averaging in the baseline calculation. PD parameters of mepolizumab, reslizumab, and placebo groups will be listed and summarized using descriptive statistics (n, mean, SD, coefficient of variation, mean, SD, minimum, median, interquartile range, and maximum) for each treatment arm.

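### The SAP runs AUEC and pAUEC to the last on-study sample (Day 63 or Day 123 by dose group), not to the Protocol's return to baseline, so comparisons across doses and pooled models partly reflect length of follow-up.

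*SAP*

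**What the plan says.** **End of the area.** SAP 4.1 gives the primary endpoint as "Peripheral blood eosinophil area under the effect curve from time zero to last onstudy timepoint". The SAP abbreviation table defines pAUEC as "percentage area under the effect curve from time zero to last on-study sample". SAP 7.3.1 adds that "AUEC and maximum decrease from baseline will be calculated for each participant using all on treatment timepoints". No SAP section truncates the area or sets a common window.

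**Follow-up.** SAP 3.1: "Subjects in Groups A, B, E, and F will follow the Schedule of Events until Day 63"; Groups C, D, G, H and I continue to Day 123. SAP 5 leaves early-termination subjects out of the parameter summaries, so every summarised subject reaches the assigned end day of the arm.

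**Metric.** SAP 7.3.1: "The primary analysis with eosinophils will use pAUEC and maximum decrease from baseline". The same sentence also lists, among optional measures, "AUEC calculation without baseline adjustment and with normalization to baseline [pAUEC"]. It does not say whether pAUEC subtracts baseline.

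**Use.** SAP 7.3.1 summarises each arm by "n, mean, SD, coefficient of variation, mean, SD, minimum, median, interquartile range, and maximum". SAP 7.5 fits linear, Emax or sigmoidal Emax models to baseline-adjusted AUEC, one drug at a time. It pools all doses with placebo and allows no covariates or random effects.

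**Protocol.** Section 5.7.2.3.1 ends AUEC at return to baseline and describes pAUEC as a change from baseline truncated at the same point. Section 5.9.6.1 uses dose-specific intervals in order to remove noise from baseline fluctuation.

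**The concern.** The window changes exactly between the second and third dose of each drug, so dose and length of follow-up are confounded. The Protocol also has unequal follow-up, but there the area stops when the effect has gone. The SAP puts end of follow-up in place of that effect-based stop.

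The primary endpoint is the values and variability of the PD metrics by dose (Protocol 4.1). The results are meant to inform dose selection (Protocol 2.2) and the design and sample size of later similarity studies (Protocol 5.9.1). If a mean, a CV or an ED50 shifts because some arms were sampled for longer, a reader comparing doses could take a feature of the schedule for a property of the drug.

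**Working it through.** **Inputs.** Sampling days from SAP Attachment A, with Day 1 as time 0: Days 1–14, weekly from 21 to 63, then 93 and 123. Group end days from SAP 3.1. Check: Days 21, 28, 35, 42, 49, 56, 63, 93 and 123 make 9 outpatient visits, which matches the SAP's stated maximum; the Day 63 arms have 7.

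**Step 1: windows.** 63 − 1 = 62 days (21 samples) and 123 − 1 = 122 days (23 samples). Ratio 122/62 = 1.97. In the long window the trapezoid weights of Days 93 and 123 are 30 and 15, so they carry 45/122 = 37% of the area. Complete suppression can score at most 62 baseline-days in A, B, E and F, but 122 in C, D, G and H.

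**Step 2: unsubtracted percent-of-baseline pAUEC.** With no effect the value is 100% at every visit: 100 × 62 = 6,200 %·day against 100 × 122 = 12,200 %·day, from the schedule alone.

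**Step 3: baseline-subtracted area, noise only.** Assume independent visit noise of constant SD s. Baseline is the mean of Day −1 and Day 1 pre-dose (SAP 7.3.1). With window T, trapezoid weights w and first weight w₀ = 0.5:

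Var/s² = T²/2 − T·w₀ + Σw²

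- Short: Σw² = 0.25 + 12 + 16 + 6×49 + 12.25 = 334.5. Var/s² = 1922 − 31 + 334.5 = 2225.5, so SD = 47.2s.
- Long: Σw² = 0.25 + 12 + 16 + 6×49 + 342.25 + 900 + 225 = 1789.5. Var/s² = 7442 − 61 + 1789.5 = 9170.5, so SD = 95.8s.
- Ratio 95.8/47.2 = 2.03.

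SAP 6.1 describes a different baseline, in which "samples from Day 1, time 0 will be used for calculating this derived metric". Then Var/s² = T² − 2T·w₀ + Σw², giving SDs of 64.2s and 128.7s, ratio 2.01.

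For an effect that is over by Day 63 the mean is the same in both windows, so the noise part of the CV rises by the same factor. If effect remains after Day 63, the means differ as well.

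**Step 4: CVs with an effect present (illustrative).** The documents give no half-life, potency, recovery time or CV, so these are assumed: an indirect-response model, dR/dt = 0.3·(1 − 0.95·C/(C + IC50)) − 0.3·R, R(0) = 1, C = dose × exp(−ln2·t/half-life). Half-life is 10, 15, 20 or 30 d and IC50 equivalent is 1.5, 3 or 6 mg (12 cells), with 25% within-subject CV and 20,000 simulated subjects per cell. The table gives CV to Day 123 over CV to Day 63 for the same 12 mg arm.

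| Metric | Between-subject variability | CV ratio |
|---|---|---|
| AUEC, baseline-subtracted | none | 1.22–2.00 |
| AUEC, baseline-subtracted | 30% in half-life and IC50 | 1.32–1.83 |
| pAUEC, baseline-subtracted | 30% in half-life and IC50 | 1.69–2.29 |
| pAUEC, unsubtracted | none | about 1.05–1.10 |

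**Step 5: pooled ED50 (illustrative).** Noise-free baseline-subtracted areas, half-life 20 d, IC50 3 mg, in baseline-days:

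| Window | 0 mg | 3 mg | 6 mg | 12 mg | 24 mg | Fitted ED50 |
|---|---|---|---|---|---|---|
| Common Day 63 | 0 | 15.6 | 23.7 | 32.5 | 40.5 | 7.3 mg |
| Common Day 123 | 0 | 18.8 | 29.5 | 42.7 | 57.1 | 10.7 mg |
| SAP (mixed) | 0 | 15.6 | 23.7 | 42.7 | 57.1 | 16.7 mg |

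The fit is E0 + Emax·dose/(dose + ED50). Over the grid, relative to common Day 123, the mixed-window ED50 is 1.07–1.45 times at half-lives of 10–15 d and 1.40–2.56 times at 20–30 d; the mixed-window Emax is 1.03–1.33 times. The common Day 63 ED50 is 0.59–0.93 times. Reslizumab doses have the same 1:2:4:8 spacing, so these ratios carry over only if its IC50 is 0.5–2 times its lowest dose.

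**Step 6: what eight per arm can show.** Two arms with equal true SDs give an SD ratio of 0.45–2.23 by chance (square roots of the 2.5% and 97.5% points of F(7,7)). Pooling four arms against four (28 df each) narrows this to 0.69–1.46.

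**The case against.** The strongest case on the other side has five parts.

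- **The unequal schedule is declared.** Both documents state it, and the Protocol itself uses dose-specific intervals. This stands: unequal follow-up is not an error. What is missing is the effect-based stop that went with it.
- **The CV effect depends on the metric.** A reader might infer that CVs double however pAUEC is read. The documents do not support that. The factor of 2.03 requires baseline subtraction, and SAP 7.3.1 does not exclude an unsubtracted percent of baseline. On that reading the CV hardly moves, and the harm is the shift in means in Step 2. A time-averaged area is not specified anywhere, so no claim is made about one.
- **The Protocol already says that pAUEC is a change from baseline.** It does. The gap is therefore an unreconciled definition rather than an absent one.
- **A Day 63 window is not the Protocol's metric either.** This stands. It omits late suppression and, at half-lives of 10–15 d on the grid, misses the Day 123 ED50 by about as much as mixed windows do. It should accompany the return-to-baseline area, not displace it.
- **This is a descriptive pilot with eight per arm.** A later similarity study would compare products at one dose over one window, where each arm's summary remains usable, and one pair of arms could not reveal the CV effect. This limits the damage to comparisons across doses and to the secondary pooled models.

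**Conclusion.** The discrepancy is clear from the text, with high confidence: the SAP's area ends at 62 or 122 days by dose group, the Protocol's ends at return to baseline, and nothing in SAP 7.5 accounts for the difference.

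Confidence in the size of the consequences is medium. The window lengths and the 6,200 versus 12,200 %·day contrast follow from the schedule alone. The 2.03 ratio assumes baseline subtraction and independent noise of constant SD. The CV ratios and ED50s with an effect present rest on an assumed model.

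A reader might infer that the arm summaries are wrong. They are not: each is valid for its own window. What fails is reading values and CVs across doses, and interpreting a pooled ED50, EC50 or Emax, as though the windows were equal. Maximum decrease from baseline is not an area and is not affected in this way.

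**What to change.** In SAP 4.1, 7.3.1 and 7.5:

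1. Define pAUEC as baseline-subtracted, in line with Protocol 5.7.2.3.1.
2. Reconcile the end of the area with Protocol 5.7.2.3.1 and 5.9.6.1 by restoring the return-to-baseline cut. State an operational rule for it, including how it applies to placebo; the Protocol gives neither.
3. Report baseline-subtracted AUEC and pAUEC from time 0 to Day 63 in all nine arms. Use them to compare values and CVs between doses and in the pooled models, and label the resulting ED50, EC50 and Emax as Day 63 quantities.
4. Keep the full-follow-up area as a sensitivity analysis.

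Maximum decrease from baseline need not change.

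The cost is SAP wording and programming: all nine arms share one sampling schedule to Day 63, so no new data are needed. The downside is that Day 63 leaves out late suppression, more at higher doses: 17, 20, 24 and 29% of the Day 123 effect area at 3, 6, 12 and 24 mg in the Step 5 example, and 3–43% over the assumed grid. It gives one consistent quantity across arms; it does not recover the Day 123 ED50.
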